Patient flow: Group education, individual social worker screening, clinical evaluation including danger sign assessment, nutritional assessment/classification/treatment, developmental screening/therapy, and condition-specific screening and treatment.

Aim 4: Compare developmental, medical, and nutritional outcomes of children who were enrolled in the PDC to other children on the main outcomes of prevalence of developmental delay as measured using the Ages and Stages Questionnaires (ASQ-3) and the prevalence of undernutrition (stunting, wasting, underweight) using anthropometric assessments.

This aim is to describe the clinical, nutritional, and developmental outcomes of vulnerable patients enrolled in PDC in comparison with:

- a. Medically vulnerable infants who did not receive PDC support. This comparison will be made using a cohort of preterm/LBW children who were born in Rwinkwavu District Hospital (RDH) before PDC started with medical, nutritional and developmental outcomes assessed at 12-36 months of age (the dataset from Aim 1).
- b. The general population of rural Rwandan children.² This comparison will be looking at developmental outcomes of children followed in PDC compared to the similar age children from the general population using UNICEF data that was collected in children ages 0-11 months and 24-35 months randomly sampled from ten rural sectors of the country.

Additional variables to be measured include (See Appendix F for data source forms of routinely collected data and Appendix A for household interview forms. All measures used in the household interview were previously used in the two comparison datasets):

- Descriptive characteristics of caregivers.
- Proportion of visits where a nutritional screening was done, danger sign screening was done, and patient had a documented ASQ within the 6 months prior to visit date.

² This existing data set was collected by UNICEF, Harvard School of Public Health, Partners In Health, and the University of Rwanda. [name] and [name] were investigators on both study teams and have access to the data.

- Proportion of children who received nutrition supplement.
- Proportion of currently enrolled children with a visit in the reference quarter whose caregivers have had at least one documented ECD counseling session
- Proportion of children with moderate or severe chronic malnutrition (height/age Z score < 2 or height/age z score < 3) at the last visit.

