- Proportion of children with moderate or severe acute malnutrition (weight/height Z score < 2 or weight/height z score < 3) at the last visit.
- Proportion of children with a completed and documented ASQ in the reference quarter failing one or more domains on the ASQ.
- Mean/median scores on the overall ASQ
- Mortality rate in both groups
- Percentage of patients lost to follow-up
- Opportunities for learning and stimulation in the home, measured by the Rwanda-adapted HOME Inventory and the Rwanda DHS Early Childhood Development Index
- Caregiver mental health, measured by the Hopkin's Symptom Checklist which has been validated in Rwanda and used in Rwanda to assess symptoms of depression and anxiety for over twenty years
- Caregiver-child interactions and discipline practices, using the Kinyarwanda version of the Observations of Mother-Child Interactions (OMCI) as well as the Rwanda DHS Child Discipline Module
- Socioeconomic status of the household, using wealth index from the Rwanda DHS
- Exposure to daily hardships and household stressors

Expanding-PDC Phase Three:

Aim 5: To evaluate the implementation of PDC during expansion, including patient characteristics, provider experiences, quality of care, cost-effectiveness, patient experiences, and patient outcomes. Findings from this aim will be used for continuous quality improvement of the PDC and informing scale-up.

Primary Outcome: The primary outcome is the proportion of study participants alive who are meeting developmental and growth milestones.

Secondary Outcomes:

- Cost-effectiveness of the PDC model
- Adherence to PDC care protocols by PDC providers
- Quality of care
- Enrollment rates, clinic retention, and barriers to care
- Patient and provider experiences
- Impact of training and mentorship in the PDC protocol
- Evaluation of improved exclusive breastfeeding prior to PDC referral
- Impact of PDC mHealth tool on protocol adherence and child growth
- Impact of PDC on child outcomes in Kirehe

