Aim 4a: Compare developmental, medical, and nutritional outcomes of children who were enrolled in the PDC to medically vulnerable children who did not receive PDC support (from Baseline Phase One)

Analysis Plan:

We will use bivariate analyses to compare the outcomes of infants who received PDC services with those who did not receive these services (the baseline data from Phase One). Developmental delay will be scored as a binary outcome looking at the proportion of children who failed one or more ASQ-3 domain at baseline to the proportion of children enrolled in PDC who failed one or more ASQ-3 domain. We will use a chi square test or fishers exact test look for significant differences in the number of children with developmental delay between children who received PDC services and those who did not. Chi squared or fishers exact tests will also be used to assess for differences in nutritional outcomes (normal, moderate, and severe malnutrition indicators) and medical outcomes among the two groups.

If we have sufficient power, we will conduct logistic regression analyses to look at predictors of developmental delay in the sample. Using backwards selection, all variables associated with developmental delay at $p < 0.10$ in bivariate will be included in the full model. We will report Odds Ratio, p-value, and 95% confidence intervals for multivariate analyses.

Aim 4b: Compare developmental, medical, and nutritional outcomes of children who were enrolled in the PDC to a sample of Rwandan children from ten rural sectors across the country.

Analysis Plan:

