We will use bivariate analyses to compare the outcomes of infants who received PDC services with a random sample of children from rural communities in Rwanda (a pre-existing dataset). Developmental delay will be scored as a binary outcome looking at the proportion of children who failed one or more ASQ-3 domain in the random sample of Rwandan children from rural areas to the proportion of children enrolled in PDC who failed one or more ASQ-3 domain. We will use a chi square test or fishers exact test look for significant differences in the number of children with developmental delay between children who received PDC services and those who did not. We will use chi squared or fishers exact test to assess for differences in nutritional (normal, moderate, and severe malnutrition indicators) among the two groups. Medical outcomes will not be assessed because the comparison database only collected data on demographics and current

developmental and nutritional status.

Expanding-PDC Phase Three:

Aim 5: Analyses of PDC expansion will be focused on descriptive analyses of process, output and selected outcome measures including, patient outcomes, quality of care, and quality improvement interventions according to defined standards, training and mentorship activities, referral rate, retention, barriers and facilitators to care, patient and provider experiences, and patient health, nutritional, and developmental outcomes. These data will be used to monitor impact of PDC on patient outcomes as well as continuous quality improvement of the model, such as the introduction of the new mHealth application to improve quality of growth monitoring. As appropriate, bivariate and multivariate analyses will be used. Qualitative analysis will use thematic coding.

Aim 5. 1. Descriptive analyses to evaluate the implementation of interventions to promote breastfeeding from as early as day one of life among newborns in the referring hospital neonatal units will focus on analysis of exclusive breastfeeding rates and proportion of newborns requiring formula pre-post quality improvement interventions.

4. Study Limitations

Pre-PDC Phase One:

1. Data is based on caregiver report and therefore subject to recall bias of the caretakers.

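### Aims 4a and 4b compare developmental delay by significance test alone: no between-group effect measure or confidence interval is planned, and the one interval promised, in a conditional Aim 4a regression, need not be for PDC

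*Combined protocol and SAP*

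**What the plan says.** Section 3.6.2 makes the prevalence of delay on the ASQ-3 a main outcome of Aim 4, alongside undernutrition. Section 3.6.4 then sets out the analysis.

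- **Aim 4a (PDC children versus the Phase One baseline).** Delay is binary, "looking at the proportion of children who failed one or more ASQ-3 domain at baseline to the proportion of children enrolled in PDC" who failed. The method is "We will use a chi square test or fishers exact test look for significant differences in the number of children with developmental delay". No effect measure or interval is attached to this comparison.
- **Aim 4a, regression.** "If we have sufficient power, we will conduct logistic regression analyses to look at predictors of developmental delay in the sample". No threshold for sufficient power is given. On building the model: "Using backwards selection, all variables associated with developmental delay at $p < 0.10$ in bivariate will be included in the full model". On reporting: "We will report Odds Ratio, p-value, and 95% confidence intervals for multivariate analyses".
- **Aim 4b (PDC children versus the rural sample).** "We will use bivariate analyses to compare the outcomes of infants who received PDC services with a random sample of children from rural communities". The test sentence for delay is the same as in Aim 4a. There is no regression and no interval.

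Two further passages bear on precision. Section 2 says that Aim 2, the predictor analysis of the Phase One sample, will not be completed because that sample is small. Section 4 warns that restricting Aim 4b to similar ages may cut the numbers and affect power.

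**The concern.** Aim 4 asks how the prevalence of delay in PDC children compares with that in two other groups. A chi-square or Fisher p-value does not give the size of a difference or how precisely it is known. That matters most when the result is not significant, and the plan itself anticipates limited numbers. In Aim 4a, a p-value above 0.05 could accompany data that fit a large benefit. In Aim 4b, it could accompany data that fit a substantial remaining deficit against the general population.

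The regression does not reliably fill the gap. It covers Aim 4a only, depends on an undefined power condition, and is framed as a search for predictors. Nothing says that PDC group is forced in. If PDC group is treated like any other candidate, a crude PDC contrast with p of 0.10 or more keeps it out of the full model, and backwards selection can remove it later. An interval for the PDC contrast is then least assured when the crude result is inconclusive, which is when it is most needed.

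**Working it through.** **No figure to reproduce.** The documents state no sample size, power, significance level, target difference or delay prevalence for Aim 4a or 4b. The check is therefore a reading of the text plus an illustration.

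**Reading.**

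| Element | Aim 4a | Aim 4b |
|---|---|---|
| Group proportions compared | yes | yes |
| Chi-square or Fisher test | yes | yes |
| Named difference or ratio for the main comparison | no | no |
| Interval for the main comparison | no | no |
| Adjusted model | only if power is sufficient | none |
| PDC group stated to be kept in the model | no | not applicable |

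**Inputs for the illustration (all assumed).** The figure of 120 per group is prompted by the count on the Phase One participant-incentive line in section 6.3. That is a budget count, not a sample size, and the line does not multiply out: 150 × 120 = 18,000, whereas the printed total is 180,000. The other group sizes and all event counts are invented.

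**Formulas.** Difference d = p1 − p0, with p1 for PDC and p0 for the comparator; SE = √[p1(1−p1)/n1 + p0(1−p0)/n0]; 95% CI = d ± 1.96 × SE. The chi-square test is uncorrected.

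*Aim 4a, 46/120 versus 60/120.* p1 = 0.3833, p0 = 0.5000, d = −0.1167. SE = √(0.001970 + 0.002083) = 0.0637. The CI is −0.1167 ± 0.1248, or −24.1 to +0.8 points. Chi-square p = 0.069; Fisher p = 0.091.

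*Aim 4b, 45/100 versus 160/400.* p1 = 0.45, p0 = 0.40, d = +0.05. SE = √(0.002475 + 0.000600) = 0.0555. The CI is 0.05 ± 0.1087, or −5.9 to +15.9 points. Chi-square p = 0.36.

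*Aim 4a, a contrast that fails the screen: 16/120 versus 24/120.* d = −6.7 points (95% CI −16.1 to +2.7), p = 0.166. This is above 0.10, so an unforced PDC term would not enter the full model, although the interval still includes a reduction of 16 points.

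**Precision over a range of sizes.** With both prevalences at 50%, the half-width is 1.96 × √(2 × 0.25/n): 17.9 points at 60 per group, 12.7 at 120 and 9.8 at 200. At 120 per group it is 7.6 points if both prevalences are 10%, and 11.6 if both are 30%.

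**Odds ratio against prevalence ratio.** For a prevalence ratio of 0.70, p1 = 0.70 × p0 and OR = [p1/(1−p1)] / [p0/(1−p0)].

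| Comparator prevalence p0 | p1 | Odds ratio |
|---|---|---|
| 10% | 7% | 0.68 |
| 30% | 21% | 0.62 |
| 50% | 35% | 0.54 |
| 70% | 49% | 0.41 |

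The odds ratio is close to the prevalence ratio at 10% and far from it at 70%.

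**The case against.** The strongest reply is that the plan does compare proportions and names prevalence as an outcome. If both proportions are published with their denominators, a reader can subtract them and even work out an interval. This stands in part. A reader might infer that the size of any PDC difference is never assured, or that the conditional odds ratio is the only estimate promised. The documents do not support either reading, because a crude point difference can be derived. What is missing is a named effect measure, its interval, and any assured adjusted estimate for PDC.

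A second reply is that the odds ratio is a standard logistic output, and that calling it misleading presumes delay is common. This also stands. Section 3.6.1 defines delay broadly, as any one domain in the range of concern or delay, which makes a high prevalence plausible. But no rate appears anywhere, and at 10% the odds ratio would mislead little.

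A third reply is that the harm is assumed. Section 4 disclaims causality and flags reduced numbers in Aim 4b, and no passage says that a non-significant result will be read as no benefit or as catch-up with the general population. That is fair, but a caution about power does not tell readers which differences the data exclude. An interval does.

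Finally, a reader might infer from the abandoned Aim 2 that the Aim 4a power condition will fail. Aim 4a adds the PDC children to the Phase One sample, so this does not follow. The condition is simply undefined.

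**Conclusion.** The point holds as a gap in planned estimation and reporting. For the main delay outcome, both comparisons rest on a test with no stated effect measure or interval. The only intervals planned belong to a conditional Aim 4a predictor model that need not retain PDC group. This part rests on the text alone and does not depend on prevalence or sample size.

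The size is illustrative. Under the assumed counts, results reported as not significant would fit a reduction of up to 24 points in Aim 4a and an excess of up to 16 points in Aim 4b. The actual widths depend on group sizes and prevalences that the documents do not give. The odds-ratio point is secondary and conditional: it matters only if delay proves common.

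**What to change.** In section 3.6.4:

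1. For Aims 4a and 4b, state that the reported result for delay is the prevalence difference and/or prevalence ratio, PDC versus comparator, with its 95% CI, whatever the p-value or power. Keep the chi-square or Fisher p-value as a supplement.
2. State that Aim 4b will be interpreted from the interval, not from the absence of significance.
3. In any adjusted Aim 4a model, force PDC group in, exempt it from the p < 0.10 screen and backwards selection, and report its estimate with a 95% CI.
4. If delay proves common, add an adjusted prevalence ratio or difference beside the odds ratio, for example from Poisson regression with robust variance or by standardisation after the logistic model.

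The cost is a few lines of analysis-plan wording and standard Stata commands on data already planned. No new data are needed.

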3.5. Selection of study population

3.5.1. Inclusion criteria

Baseline Phase One:

All infants discharged from Rwinkwavu hospital neonatal unit and born at less than 37 weeks and infants born less than 2 kilograms during the designated study period.

Post-PDC Phase Two:

All children under five years of age enrolled in PDC in Rwinkwavu District Hospital catchment area PDC clinics, will be included in Aim 3 and Aim 4b. Aim 4a will include only preterm and/or LBW (<2000g) infants for comparison with the baseline population of similar infants.

Expanding-PDC Phase Three:

All children under five years of age and their caregivers referred to or enrolled in PDC in Rwinkwavu and Kirehe District Hospital catchment areas. In addition, newborns and their caregivers from Rwinkwavu and Kirehe District Hospital catchment areas will be included as the primary referral patient population to PDC. PDC providers will also be included in some components of the evaluation.

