3.5.2. Exclusion and Stop Criteria

Pre-PDC Phase One:

1. Any infant whose family is unwilling to consent to study or decides to stop the home visit at any time.
2. Congenital heart disease per neonatal register
3. Genetic dysmorphology per neonatal register
4. Birth asphyxia per neonatal register

Post-PDC Phase Two:

1. For Aim 4a, exclusion criteria will match the Baseline Phase One exclusion criteria listed above.

Expanding-PDC Phase Three:

1. Children who do not meet inclusion criteria will be excluded.

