3.5.3 Sampling

Pre-PDC Phase One:

Potential participants will be identified and sampling will be conducted in the following manner. The study coordinator will use the Rwinkwavu neonatal registry after obtaining consent from the medical director to identify potential study participants based on the inclusion criteria outlined above. The following identifiers will be extracted from the registry: name, sex, date of birth, discharge date and mother's name. After the identification of potential participants, the patient files will be located and examined to compile the demographic information of the infants: sector, cell, village, and health center.

Post-PDC Phase Two:

All children enrolled in the PDC are eligible and no new data will be collected for Aim 3. Children will be identified through PDC patient records, which include patient registers, patient enrollment forms, routine program forms, and the electronic medical record (EMR). To complete Aim 4, additional assessments of children's growth, development, and home environment including parenting practices will be conducted through household interviews with the primary

caregivers of PDC patients. Patient names and household location will be extracted from the EMR of patients who enrolled in the PDC at least 12 months prior to data collection.

Expanding-PDC Phase Three:

All children enrolled in the neonatal units or PDC, their caregivers, and PDC providers are eligible for participation in this aim. Children will be identified through neonatal unit and PDC patient records, which include patient registers/charts, patient enrollment forms, routine program forms, and the electronic medical record (EMR).

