Our data collection is based on the use of independent data collectors. Data collection officers will be identified from the Family Strengthening Intervention Study staff (through coordination with their study coordinator) and will be trained on the use of the Ages and Stages Questionnaire as well as weight, length and head circumference measurements. Training sessions will take place at Rwinkwavu Center for Training and Operational Research. After completion of training, the data collection officers will be given a list of potential study participants. The data officers

will then contact the family's community health worker prior to making home visits and approaching the family for study participation.

Post-PDC Phase Two: All children enrolled in the PDC are eligible and the study will use routinely collected data from patient charts and EMR. In addition, patients who have been seen in the PDC clinic for 12 or more months will be contacted to participate in a household interview to be conducted by trained, independent data collectors. Patients will be identified from PDC enrollment records, and information will be extracted from patient charts for follow-up in the community (this includes caregiver name, geographic location of the household, and any relevant contact information for the household such as a phone number). Data officers will then contact the family's community health worker prior to making home visits and approaching the family for study participation.

Expanding-PDC Phase Three:

All children enrolled in the hospital neonatal units or PDC, and their caregivers, are eligible. The study will use routinely collected data from patient registers, patient charts and EMR in addition to qualitative methods. In addition, a list of PDC-eligible children prior to the opening of PDC in Kirehe (i.e., before May 2016) will be identified for household data collection to establish baseline status of high-risk infants prior to PDC. PDC providers (nurses, doctors, social workers, other parahealth professionals, volunteers) will be eligible to participate if they have been working in the PDC for at least 3 months.

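### Aim 4a tests preterm and low-birth-weight children as independent although co-twins can both enter; the error is probably small, and clustering on mother is a cheap remedy

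*Combined protocol and SAP*

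**What the plan says.** Section 3.6.4 (Analysis Plan, Aim 4a) compares the proportion of children failing at least one ASQ-3 domain between PDC children and the Phase One cohort: "We will use a chi square test or fishers exact test look for significant differences in the number of children with developmental delay". Nutritional and medical outcomes are handled by the same tests. A model is conditional: "If we have sufficient power, we will conduct logistic regression analyses to look at predictors of developmental delay in the sample". Confidence intervals are promised only there: "We will report Odds Ratio, p-value, and 95% confidence intervals for multivariate analyses".

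On who enters, section 3.5.1 says "Aim 4a will include only preterm and/or LBW (<2000g) infants for comparison with the baseline population of similar infants", and section 3.5.2 says "For Aim 4a, exclusion criteria will match the Baseline Phase One exclusion criteria listed above". Those exclusions are refused or withdrawn consent, congenital heart disease, genetic dysmorphology and birth asphyxia. Multiple births and siblings are not mentioned, and there is no rule of one child per mother.

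On what could identify a family, section 3.5.3 says for Phase One: "The following identifiers will be extracted from the registry: name, sex, date of birth, discharge date and mother's name". For Phase Two, the information taken from charts under Recruitment Methods (section 3.5.6) is described thus: "this includes caregiver name, geographic location of the household". Section 3.6.3 removes identifiers in all phases but keeps a separate linking file. It names no family or mother ID in the analysis data.

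**The concern.** A cohort selected for short gestation or low birth weight can be expected to contain multiple births, and nothing in the plan keeps co-twins out. Co-twins share a gestation and a household. Because the ASQ is scored from the caregiver's answers (section 3.6.1), they usually share a respondent too. Their results are therefore likely to be positively correlated, and a pair carries less information than two unrelated children.

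Chi-square and Fisher tests count such a pair as two independent results. At stake is the type I error of the Aim 4a comparison. If the logistic model is run, the p < 0.10 screen and the 95% intervals for predictors common to both twins are also affected. The Phase Two limitations in section 4 do not mention within-family dependence.

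**Working it through.** **No figure to reproduce.** The documents give no sample size, alpha, power or intraclass correlation for Aim 4a, so the size of the effect rests on assumptions.

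**Inputs (all assumed).**
- Share of children in twin pairs: f = 0.10–0.30.
- Within-pair correlation: ρ = 0.3–0.6.
- Two-sided alpha: 0.05.
- Group size: 120, used only for effective numbers and simulation. It comes from the incentives line of the Phase One budget (section 6.3). That line does not multiply out (150 × 120 = 18,000, against 180,000 printed), so 120 is only a stand-in.

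**Formula.** Among n children, fn/2 pairs each add 2ρp(1−p) to the variance of the number with delay. The variance is therefore np(1−p)(1 + fρ), which gives:
- design effect = 1 + fρ
- standard error ratio = √(1 + fρ)
- actual error = 2 × [1 − Φ(1.96/√(1 + fρ))]

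| f | ρ | Design effect | SE ratio | Actual error | Effective n of 120 |
|---|---|---|---|---|---|
| 0.10 | 0.3 | 1.03 | 1.015 | 5.35% | 116.5 |
| 0.10 | 0.6 | 1.06 | 1.030 | 5.70% | 113.2 |
| 0.30 | 0.3 | 1.09 | 1.044 | 6.05% | 110.1 |
| 0.30 | 0.6 | 1.18 | 1.086 | 7.12% | 101.7 |

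Over a wider range (f 0.05–0.40, ρ 0.2–0.9) the design effect runs from 1.01 to 1.36 and the error from 5.1% to 9.3%.

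**Check by simulation.** The formula assumes that the test has exactly 5% error without twins. Real tests on 2×2 tables do not. Rejection rates with no true difference, 120 per group, delay prevalence 0.5 and 40,000 replicates:

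| f, ρ | Uncorrected chi-square | Continuity-corrected |
|---|---|---|
| no twins | 4.5% | 3.2% |
| 0.10, 0.5 | 5.1% | 3.7% |
| 0.20, 0.5 | 5.6% | 4.2% |
| 0.30, 0.5 | 6.1% | 4.6% |
| 0.30, 0.7 | 7.2% | 5.5% |

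For Fisher's test, over f 0.10–0.30 and ρ 0.3–0.6 with prevalence 0.2 or 0.5, rejection is roughly 3.4% to 5.2%. The uncorrected chi-square gives roughly 4.7% to 7% over the same range.

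**Siblings in opposite groups.** Phase One children were discharged from October 2011 to October 2013, and the PDC began in April 2014, so successive siblings can fall in different groups. If a share s of each group has a sibling in the other, with correlation ρ, the variance of the difference is multiplied by 1 − sρ. With ρ = 0.3:
- s = 0.10 gives 1 − 0.03 = 0.97, and error 2 × [1 − Φ(1.96/√0.97)] = 4.7%.
- s = 0.20 gives 1 − 0.06 = 0.94, and error 4.3%.

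**The conditional model.** For a predictor with the same value in both twins, the table's ratios apply. Intervals should be 1.5% to 8.6% wider. The 10% screen becomes 2 × [1 − Φ(1.645/√1.03)] = 10.5% up to 2 × [1 − Φ(1.645/√1.18)] = 13.0%. Predictors that differ within a pair, such as sex or birth weight, do not follow this rule.

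**The case against.** The strongest reply is that the plan names Fisher's test as one of its two options, and that test is conservative enough to absorb most of the inflation. At f = 0.30 and ρ = 0.6 it stays at about nominal level. This stands as a limit on the size. It is not a planned safeguard, because the choice between the tests is left open and no continuity correction is specified.

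A second reply is that twin share and correlation are both unknown. That also stands, and reporting the number of multiples would settle much of it.

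Four stronger readings are tempting but not supported:

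- A reader might infer that the intervals for the Aim 4a comparison are too narrow. The named tests give p-values, and intervals are planned only for the conditional model.
- A reader might infer that the error always runs one way. That holds for pairs within a group, as co-twins would normally be. Siblings across the two groups make the unadjusted test conservative.
- A reader might infer that caregiver measures are counted twice. Section 3.6.2 lists them without stating whether the unit is the child or the caregiver.
- A reader might think that the adjustment costs nothing because mothers' names were collected. The comparison files are de-identified, Phase One is complete, and the linking file's stated purpose is quality checks of the electronic medical record. Clustered standard errors also need a regression, which the plan does not have for the main comparison.

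**Conclusion.** The point holds as a minor one. Aim 4a as written ignores dependence between co-twins, whom the eligibility rules allow in. With 10–30% of children in twin pairs and a correlation of 0.3–0.6, the design effect is 1.03–1.18. By normal approximation, nominal 5% becomes 5.35–7.12%. That applies to an uncorrected chi-square with pairs inside one group. Fisher's test or a continuity correction may remain near or below 5%, and split siblings pull the other way, so the net effect in this study is unknown.

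A reader might conclude that the Aim 4a result is invalid or biased on this account. The documents do not support that: the dependence affects precision and p-values and leaves the estimated difference unbiased.

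**What to change.** 1. State in section 3.6.4 how twins and siblings are handled.
2. Create an anonymous mother or household ID before identifiers are dropped. Use the linking files, with mother's name for Phase One and caregiver name and location for Phase Two, and apply one scheme to both groups.
3. Report the number of multiples in each group and the number of families with children in both.
4. Report the Aim 4a difference with a 95% confidence interval from a logistic or linear model with standard errors clustered on that ID. Fitting it to the combined data deals with pairs within a group and across groups. Use the same clustering in any predictor model. The chi-square or Fisher result can be kept alongside.
5. If no ID can be recovered for Phase One, infer twin pairs from date of birth plus village and add a sensitivity analysis with one child per mother.
6. State the unit for caregiver and household variables; one record per caregiver is the natural choice for describing caregivers.

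The cost is low but not nil. It includes the linkage work, confirmation that the linking file may be used for this purpose, and usually slightly wider intervals. Under the fallback, some unrelated infants may be paired by mistake. No new data collection is needed, and Stata, the planned software, fits these models.
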